LFT	Liver Function Test
LPS	Lipopolysaccharide
KLH	Keyhole limpet haemocyanin
OSCI	WHO Ordinal Scale for Clinical Improvement
MedDRA	Medical Dictionary for Regulatory Activities
O2	Oxygen
OTC	Over-The-Counter
PBMC	Peripheral Blood Mononuclear Cell

PIS	Patient Information Sheet
PCR	Polymerase Chain Reaction
QC	Quality Control
RNA	Ribonucleic Acid
SAE	Serious Adverse Event
SaO ₂	Oxygen Saturations
SAP	Statistical Analysis Plan
SARS-CoV-2	Severe Acute Respiratory Syndrome Coronavirus 2
SD	Standard Deviation
SF	SaO ₂ / FiO ₂ ratio
SINTAX	Small Intestinal Axis
SoA	Schedule of Activities
SpO ₂	Saturation of Oxygen
SRC	Safety Review Committee
SUSAR	Suspected Unexpected Serious Adverse Reactions
ULN	Upper Limit of Normal
WHO	World Health Organization
WOCBP	Woman of Child-Bearing Potential

1. Protocol Summary

1.1. Synopsis

Protocol Title: A Phase 2 double-blind placebo-controlled study investigating the safety and efficacy of EDP1815 in the treatment of patients hospitalized with SARS-CoV-2 Infection

Short Title: Safety and efficacy of EDP1815 in the treatment of patients hospitalized with SARS-CoV-2 Infection.

Rationale: EDP1815 is a single strain of a small-intestine targeted, systemically immune-modulating, monoclonally-expanded commensal gut bacteria. Preclinical and clinical data have demonstrated that EDP1815 reduces levels of IL-6, TNF α and IL-8, while elevating epithelial expression of IL-10 and FoxP3. At the same time, EDP1815 is well tolerated with no overall difference from placebo in human trials to date. This profile could be highly relevant with respect to treating COVID-Related Complications (CRC).

An exaggerated host immune response leads to the life-threatening complications of COVID-19 infection. The cytokine IL-6 and chemokine IL-8 have been shown to be increased in subjects hospitalized with coronaviral infections, infections with influenza A, and in secondary HLH, and their exaggerated levels are pathogenic in the development of complications such as ARDS. The host immune response is clearly important in the initial anti-viral response of the host and IL-6 in particular has been shown to be important in the early phase of the infection. A prolonged and exaggerated immune response is however associated with pulmonary complications, hospitalization and ultimately death. A therapeutic agent that does not abrogate the host immune response entirely, but instead modulates multiple pathways and returns it back to a state of immune homeostasis, could offer significant clinical benefit to subjects with coronaviral infections.

The profile of EDP1815 as an oral agent with good tolerability modulating multiple key immune pathways without blocking them completely – that is, immune normalization rather than immune suppression – could offer significant clinical benefit to patients at risk of developing serious complications secondary to COVID-19.

Table 1: Clinical Trial Objectives and Endpoints

Objectives	Endpoints
Primary	

To evaluate the effect of EDP1815 on pulmonary function as measured by the change in Oxygen Saturation (SpO₂) / Fraction of Inspired Oxygen (FiO₂) [S/F ratio]	
Change from baseline to the lowest S/F ratio measured in days 1-14

Secondary	

To evaluate the effect of EDP1815 on the development and severity of complications of COVID-19 infection	
Change in S/F ratio at days 4, 7, 10 and 14/discharge day.Percentage change in S/F ratio at days 4, 7, 10 and 14/discharge day.Percentage of participants at each level on the WHO OSCI score at days 4, 7, 14, 21 and 42.Percentage of participants with shifts from each level of the WHO OSCI score at baseline at days 4, 7, 14, 21 and 42.Percentage of participants remaining at their baseline score on the WHO OSCI (or lower) at days 4, 7, 14, 21 and 42.Percentage of participants reporting each level of the WHO OSCI score at their worst post-baseline day.The time in days spent at each participant's worst reported WHO OSCI score (excluding death).Intubation and mechanical-ventilation free survival, defined as the time in days from start of treatment to first occurrence of a WHO OSCI score of 6 or more.Overall survival, defined as the time in days from start of treatment to death by any causeNumber of days requiring oxygen therapy.Number of days with pyrexia $\geq 38^{\circ}\text{C}$.Maximum daily temperature.Minimum SpO₂ level.Maximum SpO₂ level.

To evaluate the effect of EDP1815 on length of hospitalization and recovery in participants with COVID-19	
Time to discharge, defined as the time in days from start of treatment to first occurrence of a WHO OSCI score of 2 or less.Time to oxygen saturation (SpO₂) $\geq 94\%$ on room air without further requirement for oxygen therapy.Time to recovery, defined as the time in days from symptom onset to alleviation of all COVID-19 symptoms.

To evaluate the safety and tolerability of EDP1815 in participants with COVID-19	
Incidence and severity of treatment emergent adverse events and serious adverse events.Incidence of clinically significant abnormal changes in safety laboratory parameters.
Exploratory	

To evaluate the effect of EDP1815 on the exaggerated host cytokine response to COVID-19 infection	
Change from baseline in cytokine levels (including IL-6) at day 4 and day 7 (and/or at additional timepoints if samples are available).Change from baseline in inflammatory response at day 4 and day 7 (and/or at additional timepoints if samples are available).

To identify clinical or biochemical predictors of response to EDP1815, and to confirm lack of systemic absorption.	
Statistical significance of each potential predictor-treatment interaction in exploratory models based on the final selected model for the primary efficacy analysis.To identify the presence of EDP1815 in stool and/or blood using PCR primers

Overall Design:

This is a randomized, placebo-controlled clinical study to assess the safety and efficacy of EDP1815 in patients hospitalized with COVID-19 infection. The study is designed to evaluate the efficacy of EDP1815 at reducing time to resolution of symptoms, preventing progression of COVID-19 symptoms and preventing COVID-Related Complications (CRC). The study will be fully blinded to the participants, investigator, and sponsor. This is a pilot study with a primary objective of investigating the potential of EDP1815 in the prevention of COVID-19 disease progression. The secondary objective is to evaluate multiple endpoints for clinical relevance and sensitivity, while informing the sample size for future studies. Where possible, data will be taken from assessments performed as part of the participant's routine clinical care in this pragmatic study.

Participants who are hospitalized with confirmed COVID-19 disease and are confirmed to be eligible for the study will be randomized to either the active (EDP1815) or placebo group (1:1 randomization), in addition to standard of care. Dosing will be initiated on a twice daily regime for the first 3 days (6 doses) and then once daily for the remaining 11 days (14 days total treatment course). The trial hypothesis is that treatment with EDP1815 in hospitalized patients reduces oxygen requirements by normalizing the exaggerated host immune response to COVID-19. This will be measured by assessing the ratio of the Oxygen Saturation (SpO₂) / Fraction of Inspired Oxygen (FiO₂), which is a validated measure of severity of ARDS.

Dosing will be stopped if participants are admitted to ICU, efficacy and safety data will continue to be collected according to the schedule of activities, where practical. However, if the participant is eligible for another interventional trial at this point, they may be enrolled into it, and withdrawn

from this study, after discussion with the chief investigator. Inclusion in concurrent interventional studies will not be permitted. Inclusion in observational studies in parallel to this study is allowed.

Number of Participants:

Sixty subjects will be enrolled into the study and randomized in a 1:1 ratio. A further 40 subjects may be enrolled on the request of the DMC if it was felt likely to provide further beneficial information to take forward into planning future studies.

Participant Trial Duration:

This study will consist of a 14-day treatment period followed by a 28-day post-treatment follow-up visit, as described below:

[figure not shown]
- Up to 2 days for Screening and Baseline assessment period. *Note: Due to the urgent nature of the study, screening, baseline and Day 1 assessments can occur on the same day. Eligible patients will be randomized and dosed as soon as possible after eligibility is confirmed.*
- A 14-day treatment period (treatment will be stopped if the participant is admitted to ICU).
- A 28-day post-treatment period, with final follow-up via telephone assessment at Day 42.

Number of Centers:

The study will be run at multiple centers in the United States.

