2.2. Mechanism of Action

EDP1815 is an orally administered pharmaceutical preparation of a single strain of *Prevotella histicola* isolated from the duodenum of a human donor. *Prevotella* is the genus of human commensal organisms commonly found on oral, nasopharyngeal, gastrointestinal, and genitourinary mucosal surfaces. It has been found in all human population groups studied so far. EDP1815 is currently in phase 2 clinical development and has European and US approval to initiate a multinational psoriasis study, scheduled for 2Q2020.

Preclinical and clinical data have demonstrated that EDP1815 can systemically suppress IL-6, TNF α and IL-8, while elevating epithelial expression of IL-10 and FoxP3. At the same time, EDP1815 is well tolerated with no overall difference from placebo in human trials to date. This profile could be highly relevant with respect to treating CRC.

EDP1815 works via the small intestinal axis (SINTAX): a network of anatomical and functional connections between the small intestine and the rest of the body. SINTAX links small intestinal mucosal immunology with systemic inflammation, accessible with oral medicines. EDP1815 is non-pathogenic, not genetically modified, does not colonize or persist in the gut, and does not modify the colonic microbiome. It acts locally in the gut - which is, in effect, on the outside of the body - but has pharmacodynamic activity throughout the inside of the body modulating the immune system without any systemic exposure.

EDP1815 is not systemically absorbed and there are no expected ADRs. Safety and tolerability have been indistinguishable from placebo, with no SAEs or AEs of severe intensity reported. The nature of the pharmaceutical preparation of EDP1815 ensures that there is no unwanted persistence of the drug after administration. It does not modify the colonic microbiome as assessed by 16S ribosomal RNA sequencing of stool samples from patients, and the drug is undetectable in stool samples once dosing has ceased. Importantly, there has been no increased risk of infections observed in the phase 1 program.

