2.4. Benefit/Risk Assessment

EDP1815 is a specific pharmaceutical preparation of *Prevotella histicola*, a natural human commensal organism, commonly found on oral, nasopharyngeal, GI, and genito-urinary mucosal surfaces.

EDP1815 is being investigated for its potential benefit in immunoinflammatory disorders, including the cytokine storm associated with COVID-19. There is significant morbidity and mortality benefit to be derived from reducing COVID-Related Complications.

The safety profile of EDP1815 has been indistinguishable from placebo in both the EDP1815-101 and EDP1815-102 studies, with no serious adverse events (SAEs) or adverse events (AEs) of severe intensity reported in either study. Mild and transient AEs have included headache and diarrhoea.

3. Objectives and Endpoints

Table 2: Clinical Trial Objectives and Endpoints

Objectives	Endpoints
Primary	

To evaluate the effect of EDP1815 on pulmonary function as measured by the change in Oxygen Saturation (SpO₂) / Fraction of Inspired Oxygen (FiO₂) [S/F ratio]	
Change from baseline to the lowest S/F ratio measured in days 1-14
Secondary	
To evaluate the effect of EDP1815 on the development and severity of complications of COVID-19 infection 
Change in S/F ratio at days 4, 7, 10 and 14/discharge day.Percentage change in S/F ratio at days 4, 7, 10 and 14/discharge day.Percentage of participants at each level on the WHO OSCI score at days 4, 7, 14, 21 and 42.Percentage of participants with shifts from each level of the WHO OSCI score at baseline at days 4, 7, 14, 21 and 42.Percentage of participants remaining at their baseline score on the WHO OSCI (or lower) at days 4, 7, 14, 21 and 42.Percentage of participants reporting each level of the WHO OSCI score at their worst post-baseline day.The time in days spent at each participant's worst reported WHO OSCI score (excluding death).Intubation and mechanical-ventilation free survival, defined as the time in days from start of treatment to first occurrence of a WHO OSCI score of 6 or more.Overall survival, defined as the time in days from start of treatment to death by any causeNumber of days requiring oxygen therapy.Number of days with pyrexia $\geq 38^{\circ}\text{C}$.Maximum daily temperature.Minimum SpO₂ level.Maximum SpO₂ level.

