7.1 Discontinuation from Study Treatment and/or Withdrawal from the Study

Participants may discontinue from study treatment or withdraw from the study at any time and for any reason without prejudice to their future medical care by the investigator or at the study site. Every effort should be made to keep participants in the study. The reasons for participants discontinuing treatment and/or withdrawing from the study will be recorded in the CRF. A participant may discontinue from the study drug or withdraw for the following reasons:

1. The participant does not meet the protocol inclusion or exclusion criteria.
2. The participant is non-compliant with the protocol.
3. The participant is admitted to ICU. At this point, dosing for this individual subject will be stopped, but they will remain in the study until Day 42 for data collection where practical. However, if the subject is eligible for another interventional trial, they may be enrolled into this trial after discussion with the chief investigators. The participant is deemed to have completed this study at the point of signing the informed consent of this other study.
4. The participant has a serious or intolerable AE that in the investigator's opinion requires discontinuation from study treatment or withdrawal from the study (see section 7.2).
5. The participant has laboratory safety results that reveal clinically significant changes from the baseline values that are not, in the opinion of the investigator, explained by COVID-19 infection or CRCs.
6. The participant is lost to follow-up.
7. Other reasons (e.g. pregnancy).
8. The participant withdraws consent, or the investigator or sponsor decides to discontinue the participant's participation in the study.

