8.3. Adverse Events and Serious Adverse Events

The definitions of an AE or SAE can be found in Appendix 3.

AEs will be reported by the participant (or, when appropriate, by a caregiver, surrogate, or the participant's legally authorised representative). Due to the nature of the patient population and disease only SAEs and AEs of severe (CTCAE Grade 3) and potentially life threatening (CTCAE Grade 4) intensity will be documented in the CRF. AEs of mild (CTCAE Grade 1) or moderate (CTCAE Grade 2) intensity should be documented in the medical notes. However, adverse events relating to nausea, vomiting, diarrhoea, bloating and abdominal pain of any grade will be recorded and assessed as an adverse event.

The investigator and any qualified designees are responsible for detecting, documenting, and recording events that meet the definition of an AE or SAE and remain responsible for following up AEs that are serious, considered related to the study intervention or study procedures, or that caused the participant to discontinue the study intervention (see Section 7).

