10.2 Adverse Events

Due to the nature of the participant participation and disease, only serious AEs (SAEs), AEs of severe (Common Terminology Criteria for Adverse Events (CTCAE) Grade 3) and potentially life-threatening (CTCAE Grade 4) intensity, and AEs relating to nausea, vomiting, diarrhea, bloating and abdominal pain of any grade will be documented in the CRF. Other AEs of mild (CTCAE Grade 1) or moderate (CTCAE Grade 2) intensity are to be documented in the medical notes.

Only treatment emergent AEs and SAEs reported in the CRF will be included in the summaries, pre-treatment AEs and SAEs reported in the CRF will be included in the listings of all AEs.

All AEs will be coded using version 23.0 of MedDRA.

Treatment-emergent AEs will be summarized by treatment, system organ class (SOC) and preferred term. Summary tables will contain the number and percentage of participants and the number of events. A participant who has multiple events in the same SOC or the same preferred term will be counted only once in the participant counts but all events will be counted in the event counts. Adverse event

summaries will be sorted by the internationally agreed SOC order (Table 15) and decreasing incidence of preferred term within SOC in the EDP1815 column.

The above summary will be repeated for Treatment Phase AEs and for Follow-up Phase AEs.

AEs considered related to study treatment will also be summarized by treatment, SOC and preferred term in the same manner as described above.

All AEs, SAEs, fatal AEs, AEs leading to discontinuation of study treatment or withdrawal from the study will be listed separately by participant. Adverse events of special interest will be flagged in the listings.

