16.3 Safety

16.3.1 Tables

Number	Title	Population	Early Stop	Programming notes ¹
14.3.1.1.1	Summary of All TEAEs by System Organ Class and Preferred Term	Safety	Yes	DMC-Unblinded
14.3.1.1.2	Summary of Treatment Phase TEAEs by System Organ Class and Preferred Term	Safety	Yes	DMC-Unblinded
14.3.1.1.3	Summary of Follow-up Phase TEAEs by System Organ Class and Preferred Term	Safety	Yes	DMC-Unblinded
14.3.1.1.4	Summary of All TEAEs by Age Group, System Organ Class and Preferred Term	Safety		DMC-Safety Only produced if participants aged >65 are permitted to enter the study
14.3.1.2	Summary of Treatment-Related TEAEs by System Organ Class and Preferred Term	Safety	Yes	
14.3.2.1	Summary of Serious TEAEs by System Organ Class and Preferred Term	Safety	Yes	DMC-Unblinded
14.3.2.2	Summary of TEAEs Leading to Permanent Discontinuation from Study Drug by System Organ Class and Preferred Term	Safety	Yes	
14.3.2.3	Summary of TEAEs Leading to Withdrawal from the Study by System Organ Class and Preferred Term	Safety	Yes	
14.3.2.4	Summary of Fatal TEAEs by System Organ Class and Preferred Term	Safety	Yes	

Number	Title	Population	Early Stop	Programming notes ¹
14.3.2.5.1	Summary of TEAEs of Special Interest by Preferred Term and CTCAE Grade	Safety	Yes	DMC-Unblinded
14.3.2.5.2	Summary of TEAEs of Special Interest by Preferred Term and Relationship to Study Drug	Safety	Yes	DMC-Unblinded
14.3.4.1.1	Summary of Change from Baseline in Hematology	Safety	Yes	
14.3.4.1.2	Summary of Shifts from Baseline to Worst-case Post-Baseline with Respect to the Normal Range in Hematology	Safety	Yes	DMC-Unblinded
14.3.4.1.3	Summary of Shifts from Baseline to Worst-case Post-Baseline with Respect to the PCI Criteria in Hematology	Safety	Yes	DMC-Unblinded
14.3.4.1.4	Summary of Shifts from Baseline to Worst-case Post-Baseline with Respect to the PCI Criteria in Hematology, by Age Group	Safety		DMC-Safety Only produced if participants aged >65 are permitted to enter the study
14.3.4.2.1	Summary of Change from Baseline in Clinical Chemistry	Safety	Yes	
14.3.4.2.2	Summary of Shifts from Baseline to Worst-case Post-Baseline with Respect to the Normal Range in Clinical Chemistry	Safety	Yes	DMC-Unblinded
14.3.4.2.3	Summary of Shifts from Baseline to Worst-case Post-Baseline with Respect to the PCI Criteria in Clinical Chemistry	Safety	Yes	DMC-Unblinded

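### Non-serious, non-laboratory Grade 1-2 AEs outside five GI symptoms stay off the CRF even when judged drug related or when they stop treatment, so the SAP tables for such events are incomplete

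*Protocol*

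**What the plan says.** Under the objective of evaluating safety and tolerability, Protocol Sections 1.1 and 3 define the endpoint as "Incidence and severity of treatment emergent adverse events and serious adverse events". No grade limit is attached.

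Protocol Section 8.3 sets the capture rule: "only SAEs and AEs of severe (CTCAE Grade 3) and potentially life threatening (CTCAE Grade 4) intensity will be documented in the CRF". For the rest, "AEs of mild (CTCAE Grade 1) or moderate (CTCAE Grade 2) intensity should be documented in the medical notes". The one stated exception is abdominal pain, bloating, diarrhoea, nausea and vomiting, which are recorded at any grade. Appendix 3 (Section 10.3) and SAP Section 10.2 repeat the rule, and all three places give the same reason: the kind of patient and the disease under study.

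SAP Section 10.2 then fixes the data source: "Only treatment emergent AEs and SAEs reported in the CRF will be included in the summaries". The output list in SAP Section 16.3.1 includes Table 14.3.1.2 on treatment-related TEAEs, Table 14.3.2.2, titled "Summary of TEAEs Leading to Permanent Discontinuation from Study Drug by System Organ Class and Preferred Term", and Table 14.3.2.3, its counterpart for withdrawal from the study. None of these titles mentions a grade restriction.

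Among the reasons for stopping treatment or leaving the study, Protocol Section 7.1 lists "The participant has a serious or intolerable AE" that the investigator thinks requires it. The word for intolerable events carries no grade.

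**The concern.** A grade floor on AE recording is a reasonable economy in a hospitalised COVID-19 population, where mild unrelated events are plentiful and say little. That argument does not reach two kinds of event: those the investigator attributes to the study drug, and those that end dosing. These bear directly on tolerability whatever their grade, and the SAP has dedicated tables for them. If the CRF never receives the low-grade ones, the tables will be short of events that their titles promise, and nothing on the page will tell the reader so.

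At stake is what may be concluded from this pilot about tolerability. An empty or sparse related-TEAE table could be read as no related events of any grade, when for most terms it can show only serious or Grade 3-4 events. Table 14.3.1.1.1, which claims to cover all TEAEs, has the same difficulty: it puts any-grade counts for five symptoms beside counts that start at Grade 3, or at seriousness, for nearly everything else.

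**Working it through.** No arithmetic applies: the point depends on which events are recorded, not on a rate, SD or sample size. The check follows each type of event from the capture rule (Protocol Section 8.3, Appendix 3, SAP Section 10.2), through the SAP's restriction to CRF-reported events, to the output list (SAP Sections 10.3 and 16.3.1).

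| Type of event | AE record on the CRF? | In the SAP's AE tables? |
|---|---|---|
| SAE, any grade | Yes | Yes |
| Grade 3-4, any term | Yes | Yes |
| Grade 1-2, one of the five GI symptoms | Yes | Yes |
| Clinically relevant laboratory change, Grade 1-2 | Yes under Protocol 8.2.5, no under Protocol 8.3 | Unclear until reconciled |
| Other non-serious Grade 1-2, unrelated, dosing continues | No | No (the intended economy) |
| Other non-serious Grade 1-2, judged related | No | Absent from 14.3.1.2 |
| Other non-serious Grade 1-2, stops dosing or leads to withdrawal | No, only the reason for stopping | Absent from 14.3.2.2 or 14.3.2.3 |

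Three steps decide the last two rows.

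1. Is there an exemption elsewhere? Section 8.3 does single out AEs that are related or that caused discontinuation, but only to say that the investigator must follow them up. It does not lift the grade floor for CRF entry. No such clause appears in Appendix 3 or the SAP.

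2. Can an AE below Grade 3 stop treatment? Yes. Section 7.1 attaches no grade to intolerability and lets participants stop for any reason. Section 7.2.1 also ends dosing permanently if an AE recurs after a restart, with no grade given for the recurrence; the Grade 3 episode that led to the pause would already be on the CRF.

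3. Where does such a stop appear? Section 7.1 requires the reason to be recorded in the CRF. SAP Section 8.1 tabulates reasons by arm (Table 14.1.1.1), and Listings 16.2.1.2 and 16.2.1.3 show them. Neither document links that reason to a coded term, a CTCAE grade or a causality assessment, which an AE record would supply.

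The laboratory row is a separate inconsistency. Section 8.2.5 tells the investigator to enter clinically relevant laboratory changes in the AE section of the CRF without a grade limit, while Section 8.3 sends Grade 1-2 events outside the five symptoms to the medical notes.

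**The case against.** The strongest reply is that this is a disclosed and reasoned choice in a descriptive pilot that calls itself pragmatic. The rule is the same in three places, a reason is given, and SAP Section 10.2 states it just before describing the tables. All of that stands, and it is why the grade floor should not be removed. It does not explain why related or treatment-stopping events fall under the floor.

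Much is also captured by other routes. SAEs of any grade and all Grade 3-4 events reach the CRF. Most laboratory values are flagged from CTCAE Grade 2 (SAP Section 10.4). The five GI symptoms have their own tables by grade and by relationship (14.3.2.5.1 and 14.3.2.5.2), so they can be separated from the overall counts. The outpatient diary records AEs and is listed (16.2.6.11), and concomitant medications are recorded with the reason for use. This limits the loss, but neither the diary nor the medication record feeds the AE tables.

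On treatment stops, Section 7.1 refers the reader to Section 7.2, where the AE-based rules start at Grade 3 for a pause and Grade 4 for permanent cessation. A stop for a lower-grade event is therefore an edge case. That stands too.

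A reader might go further and infer that the plan is blind to the drug's non-GI profile, with headache as the example: of earlier studies, Section 2.4 says "Mild and transient AEs have included headache and diarrhoea", Section 2.2 says "with no SAEs or AEs of severe intensity reported", and only diarrhoea is on the any-grade list. The documents do not support that much. The sentence in Section 2.4 is not an exhaustive profile, and the same section describes safety as indistinguishable from placebo. Where headache is an expected symptom of the disease, Appendix 3 says it is not an AE unless more severe than expected, so a rule to record every headache would sit awkwardly with that definition. Whether to list headache at any grade is a debatable trade-off, not a gap.

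**Conclusion.** The point holds in a narrow form. Non-serious, non-laboratory Grade 1-2 AEs outside the five GI symptoms cannot enter Tables 14.3.1.2, 14.3.2.2 or 14.3.2.3, even when they are exactly what those tables are titled to show, and the endpoint and titles do not disclose the cut.

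The size can be stated by category but not by count. For this class of event the three tables are empty by rule. The documents give no rate for such events, so the number lost could be zero or more. For treatment stops it is probably small, given Section 7.2, and the stop itself stays visible in the disposition outputs.

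It would be too strong to say that the tables will look clean outside the GI system whatever happens: serious and Grade 3-4 non-GI events are recorded, and some laboratory events may be recorded below Grade 3 through Section 8.2.5. It would also be too strong to say that treatment-stopping events disappear. The conclusion assumes that sites follow the capture rule as written and that no CRF instruction outside these two documents adds the missing exemption.

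**What to change.** Keep the grade floor. In Protocol Section 8.3, Appendix 3 and SAP Section 10.2, add that any AE judged related to study drug, or leading to interruption or discontinuation of study drug or to withdrawal from the study, is recorded on the CRF at any grade.

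State the resulting capture rule in the safety endpoint (Protocol Sections 1.1 and 3), and as a footnote to Table 14.3.1.1.1 and to Tables 14.3.1.2, 14.3.2.2 and 14.3.2.3. Reconcile Protocol Section 8.2.5 with Section 8.3, so that sites know whether a clinically relevant laboratory change below Grade 3 belongs in the AE section.

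The cost is wording in both documents and a few more CRF entries. The assessments already exist: Appendix 3 requires a causality judgement for every AE, and Section 7.1 requires the reason for stopping to be recorded. If the capture rule cannot be changed, the endpoint wording and footnotes alone would make the tables honest about what they contain, but would not make them complete.
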